STUDY PROTOCOL AND STATISTICAL ANALYSIS PLAN

Official title: Problem-Solving Training for Care Partners of Adults with Traumatic Brain Injury

NCT number: NCT03739450

IRB approved date: 06-02-20

**The University of Texas Southwestern Medical Center at Dallas
Institutional Review Board**

Protocol Template (for Investigator Initiated Studies)

Title: Problem-Solving Training for Care Partners of Adults with Traumatic Brain Injury

1. Introduction and Purpose: The purpose of this project is to:

AIM 1: Assess the feasibility of delivering up to 6 sessions of Problem Solving Training (PST) to care partners of individuals with traumatic brain injuries (TBI) during the inpatient rehabilitation stay.

- **Hypothesis 1a:** Care partners will complete at least three intervention sessions (in person and/or via telephone) prior to discharge from inpatient rehabilitation and will report high satisfaction.
- **Aim1a:** Determine the number of sessions that it is feasible to complete during the inpatient rehabilitation stay and factors associated with non-compliance.

AIM 2: Assess the efficacy of PST plus TBI-specific education compared to TBI-specific education alone for improving the outcomes of care partners of individuals with TBI.

- **Hypothesis 2a:** PST will reduce care partners' burden and depressive symptoms (primary), while improving care partners' coping skills (secondary) at one-month post discharge more than TBI-specific education alone.
- **Hypothesis 2b:** Effects of the PST intervention on care partner burden, depressive symptoms, and coping will be maintained at 6 months post-intervention.

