Problem-Solving Training (PST) is an evidence-based, self-management approach that teaches a simple, systematic method for evaluating problems, generating and selecting solutions, creating and implementing realistic goals and action plans, and evaluating whether those plans effectively addressed the specific goal.^{15,16} A growing body of evidence indicates that PST post-discharge is associated with reduced distress among care partners of adults with TBI.¹⁷⁻¹⁹ Problems previously seen as overwhelming are regarded as solvable and manageable when approached in a stepwise

fashion using PST, thereby reducing perceived burden and emotional distress. PST empowers care partners to be active participants in directing health and rehabilitation services.

We anticipate that care partners will be able to complete a minimum of 3 sessions during the inpatient rehabilitation stay, with the goal of completing 6 sessions. We also anticipate that PST + Education will be more effective than Education alone for reducing caregiver burden and depressive symptoms and improving positive coping among care partners. This study will provide evidence for effective strategies to support and improve outcomes for care partners during the transition from hospital to home. This will benefit the TBIMS as a whole by providing an evidence-based and feasible intervention for care partners, upon whom the TBIMS relies heavily for participant enrollment and data collection, in addition to the ongoing support that care partners provide to the primary beneficiaries of TBIMS services, individuals with TBI. PST is an evidence-based, self-management approach with a strong theoretical foundation that has demonstrated efficacy for care partners of individuals with disabilities. Early work indicates that it is also effective for care partners of adults with TBI. However, there are no studies evaluating whether delivery of PST to care partners is feasible and effective during inpatient rehabilitation. The proposed project builds upon this foundation of evidence to address this critical gap in the literature.

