Description of Interventions: Care partners in the intervention group will receive PST training in addition to TBI-specific education. Participants in the Control group will receive TBI-specific education alone. Both groups will receive up to 6 sessions, delivered in person or via telephone. Trained members of the research team with master's level education or equivalent experience will provide both interventions using a specific curriculum that has been validated in our previous research studies. These activities will take place prior to discharge from inpatient rehabilitation. Sessions will occur face-to-face whenever possible and over the telephone circumstances when face-to-face is not feasible. Up to 6 sessions will be delivered, with a target of 2/week, maximizing the likelihood of completing all sessions before discharge and providing sufficient time for care partners to put their plans into action between sessions. Sessions will conclude at discharge, with the exception of completing the final session via telephone if it was not completed prior to discharge. We will audio record the delivery of the sessions to ensure fidelity and evaluate feasibility, and document completion, reasons for non-compliance/non-completion, method of delivery, session length, participant engagement, and a brief summary of the PST steps covered during each session.

A trained research staff, blinded to intervention allocation, will perform all assessments in person, via telephone, or will send the assessments electronically to the participant through RedCap at baseline, 1-month, and 6-months post-intervention. Blinding will be ensured by allocating to group assignment after baseline assessment is complete, having different staff performing assessments vs delivering

the intervention, scheduling meetings with assessors and interventionists separately, and instructing participants to not discuss the intervention with the person calling to complete follow-up assessments. We will collect data on demographic (age, gender, race, ethnicity, education), care partners relationship information (nature, duration, living status), and outcome measures assessing mood, caregiver burden, coping skills, self-efficacy, and satisfaction with the intervention (data collection forms for each assessment time point are attached in a later section).

5. Sub-Study Procedures: n/a

6. Criteria for Inclusion of Subjects:

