12. Procedures to Maintain Confidentiality: In order to assure participant confidentiality, all participants will be assigned a unique study identification number. Links to identifiers will be maintained at UTSW by study staff. All databases will use the subject ID number rather than private health information. The only exception will be that the RedCap database will include the participant e-mails and information necessary to obtain eConsents. This is necessary in order to send out the assessments via RedCap and to obtain participant consent through RedCap. PHI in RedCap will be marked as patient health information, for which only study personnel will have access. Signed consent forms and all paper study documents will be maintained by the PI and co-investigators at participating centers behind a locked door in a locked file cabinet or in RedCap.

13. Potential Benefits: Participants receiving the PST intervention may benefit from reduced symptoms of burden and depression and improvements in adaptive coping. Participants receiving Education may also benefit from reduced symptoms or greater self-efficacy. Further, from this study, we hope to improve clinical programming to better support care partners of patients in acute hospitalization and inpatient rehabilitation. This could lead to improving not only the long-term health and well-being of care partners, but also of individuals with acquired disabilities.

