14. Biostatistics: Specific Aim 1: The primary outcome is the total number of sessions completed prior to discharge, with a threshold of 80% of participants completing a minimum of 3 sessions as an indicator of feasibility. We will descriptively present reasons for non-compliance and explore factors associated with non-compliance (e.g. demographics, hospital length of stay, etc.). The secondary outcome for feasibility is satisfaction, with an item mean of ≥ 3.5 on the CSQ-8 as an indicator of high satisfaction. **Specific Aim 2:** To test our first hypothesis, we will use intent-to-treat analyses to measure the pre-post-test differences in each outcome between baseline and 1-month follow-up using a paired t-test or Wilcoxon signed rank test as appropriate. To address our second hypothesis, we will use intent-to-treat analyses to measure the pre-post-test differences in each outcome between baseline and 6-month follow-up (all participants) using paired t-tests or Wilcoxon signed rank tests. Effect sizes will be calculated and interpreted as follows: <0.2 =no/minimal effect; $0.2-0.5$ = small effect; $0.5-0.8$ =medium effect; ≥ 0.8 =large effect.

References

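### Does the 80% feasibility rule leave open whether Education-only attendance counts towards PST feasibility?

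*Combined protocol and SAP*

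**What the plan says.** Section 14, under Specific Aim 1, takes the number of sessions completed before discharge as the primary feasibility outcome, "with a threshold of 80% of participants completing a minimum of 3 sessions as an indicator of feasibility". Satisfaction is secondary, with a CSQ-8 item mean of at least 3.5 counted as high. Neither threshold names an arm.

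Section 1 states the aim as "Assess the feasibility of delivering up to 6 sessions of Problem Solving Training (PST"), directed at care partners during the inpatient stay. Hypothesis 1a reads: "Care partners will complete at least three intervention sessions (in person and/or via telephone) prior to discharge from inpatient rehabilitation". Section 2 (Background), in its account of PST, says: "We anticipate that care partners will be able to complete a minimum of 3 sessions during the inpatient rehabilitation stay".

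Section 4 (Description of Interventions) adds: "Both groups will receive up to 6 sessions, delivered in person or via telephone". It also says: "Participants in the Control group will receive TBI-specific education alone". Staff "will provide both interventions using a specific curriculum". Section 13 refers to controls in the same terms: "Participants receiving Education may also benefit from reduced symptoms or greater self-efficacy".

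**The concern.** Aim 1 asks whether PST can be delivered before discharge. The rule that answers it counts participants and sessions without qualification. Controls are called participants, they can complete 3 or more sessions, and their programme is one of the two described as interventions. Nothing in the sentence itself keeps a control with three education sessions out of the numerator and denominator.

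If the arms were pooled, good attendance in the Education arm could carry a PST arm that misses 80%, and poor attendance there could sink a PST arm that reaches it. If the choice were made only once attendance was known, it could be made to suit the result. The CSQ-8 threshold is open in the same way. A smaller question sits inside the PST arm: it receives education as well as PST, and the plan does not say how its sessions divide between the two.

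**Working it through.** **Is there a figure to reproduce?** No. The 80% is a set criterion. The documents give no sample size, allocation ratio or expected completion rate, so every rate and arm size below is an assumption.

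**How far the readings can diverge.** With a share *w* of participants in the PST arm, pooled rate = *w* × PST rate + (1 − *w*) × Education rate. At 1:1, *w* = 0.5.

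- PST 22/30, Education 27/30: PST arm 22/30 = 73%, fails; pooled (22 + 27)/60 = 49/60 = 82%, passes.
- PST 26/30, Education 20/30: PST arm 26/30 = 87%, passes; pooled (26 + 20)/60 = 46/60 = 77%, fails.

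**Chance of passing.** Passing means an observed proportion of at least 80%. At 30 per arm that is 24 or more of 30 for the PST arm (binomial tail), or 48 or more of 60 pooled (sum of two independent binomials).

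| True completion, PST / Education | PST arm only | Pooled | Difference (points) |
|---|---|---|---|
| 70% / 90% | 16% | 58% | 42 |
| 85% / 70% | 85% | 39% | 46 |
| 70% / 80% | 16% | 23% | 7 |
| 75% / 80% | 35% | 39% | 4 |

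From 20 to 50 per arm, the 70/90 row runs from 24% to 8% (PST arm) against 59% to 56% (pooled). The 85/70 row runs from 83% to 88% against 44% to 32%. A larger trial does not close the gap.

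The two readings also differ when the arms have equal rates: 16% against 6% at 70/70, and 85% against 89% at 85/85. That reflects only the larger pooled sample. In both cases pooling gives the more reliable answer, so these rows are not evidence that PST feasibility is misstated.

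**Which reading the text supports.**

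1. *Place.* The rule is filed under Specific Aim 1, and Section 1 defines that aim as delivery of PST.
2. *Data named for the purpose.* Section 3 describes the PST sessions and then says those data serve to judge whether that intervention can feasibly be delivered. This settles session type better than denominator, because Section 3 leaves the control arm out of its description.
3. *Labels.* Section 4 does call both programmes interventions, but the same paragraph sets the intervention group, which gets PST, against the control group. On that labelling, the sessions in Hypothesis 1a are those of the PST arm.
4. *Contrast within Section 14.* The 6-month analysis is explicitly marked as covering all participants; the feasibility rule carries no such mark. This is a weak pointer, but it points the same way.
5. *Pooling.* No sentence asks for it.

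**What is open about sessions.** Timing (before discharge) and mode (in person or by telephone) are stated. Only session type within the PST arm is left, and counting education content there could only overstate PST completion. Section 4 has staff record completion and the PST steps covered at each session, so PST sessions can be identified from planned data.

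**The case for a change.** The strongest reply is that an aim does not define an analysis set. A pass/fail threshold should name its denominator, and here the ordinary words do not: participants covers controls, and interventions covers education. Section 3 is imperfect support, since it describes every participant as receiving PST. Intent-to-treat is stated only for Aim 2, so the plan does not say whether care partners with no sessions count in the 80%. One sentence would settle all of this with no new data.

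Much of that stands. The rule names no arm, the CSQ-8 threshold names none, and the arithmetic is right. What does not stand is the step from silence to a real risk of misstatement. That step needs an analyst to pass over the aim the rule is filed under, and it needs completion to differ markedly between arms. Section 4 gives both arms the same maximum number of sessions, target frequency, delivery modes, staff qualifications and setting, so nothing in the documents points to gaps of 15 to 20 points. The threshold is also described as an indicator of feasibility, not as a stopping or go/no-go rule, and because completion is documented, results by arm stay recoverable.

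**Conclusion.** No change to the plan is called for. The wording gap is real, but a competent analyst fills it in one way: the 80% indicator and the CSQ-8 threshold are read on care partners randomised to PST + Education, with Education attendance reported for comparison. Writing that down would record the analysis already implied and would not alter it.

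On the assumed figures (1:1, 30 per arm), pooling moves the chance of passing by 42 to 46 points when true completion differs by 15 to 20 points, and by 4 to 7 points when it differs by 5 to 10. Those shifts arise only if the arms are pooled, which the plan nowhere asks for. The conclusion rests on reading Section 14 together with Sections 1, 3 and 4. It would change if the sponsor in fact meant to apply the threshold to both arms combined.

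### Aim 2 asks whether PST + Education beats Education alone, but the only planned tests are paired before-after tests with no arm comparison

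*Combined protocol and SAP*

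**What the plan says.** Section 1 (Introduction and Purpose) sets Aim 2 as a comparison: "Assess the efficacy of PST plus TBI-specific education compared to TBI-specific education alone". Hypothesis 2a expects PST to reduce burden and depressive symptoms (primary) and to improve coping (secondary) "at one-month post discharge more than TBI-specific education alone". Hypothesis 2b states that "Effects of the PST intervention on care partner burden, depressive symptoms, and coping will be maintained at 6 months post-intervention". Section 2 (Background) anticipates that "PST + Education will be more effective than Education alone for reducing caregiver burden and depressive symptoms". Section 4 (Study Procedures) describes a randomised controlled trial of the two arms, blocked and stratified by site.

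Section 14 (Biostatistics) holds all the analysis text. For the first Aim 2 hypothesis it will "measure the pre-post-test differences in each outcome between baseline and 1-month follow-up using a paired t-test or Wilcoxon signed rank test as appropriate". For the second it names the same tests, "between baseline and 6-month follow-up (all participants) using paired t-tests or Wilcoxon signed rank tests". Both are labelled intent-to-treat. Bands are then given for interpreting effect sizes, without saying how those are computed. No two-sample test, ANCOVA, mixed model or arm-by-time term appears anywhere.

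**The concern.** A paired t-test or signed rank test is a one-sample test on each person's change. That change combines any PST effect, any effect of education, the natural course over the period, and regression to the mean. Only the randomised control arm can separate the first of these from the rest, and the planned tests do not use it.

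Two wrong conclusions follow.

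- **False claim of benefit.** Section 13 (Potential Benefits) itself expects some shared improvement: "Participants receiving Education may also benefit from reduced symptoms or greater self-efficacy". A fall in scores in the PST arm, or in both arms pooled, could then be reported as efficacy when PST adds nothing.
- **Missed benefit.** Baseline is taken while the patient is still an inpatient, and section 2 describes the move home as the period when burden is greatest. PST could work by preventing a rise that occurs under education alone. A before-after test in the PST arm would then show no change.

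**Working it through.** **Step 1: match each hypothesis to its test.**

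| Hypothesis (section 1) | Contrast needed | Test named (section 14) | Uses arm? |
|---|---|---|---|
| 2a, 1 month | PST + Education minus Education | Paired t or signed rank, baseline vs 1 month | No |
| 2b, 6 months | Whether the PST effect persists | Paired t or signed rank, baseline vs 6 months | No |

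Section 14 does not say whether the tests are run in each arm or on both arms together. Neither option gives a between-arm contrast.

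**Step 2: inputs for an illustration.** The plan gives no sample size, power, alpha, SD, target effect or allocation ratio for Aim 2, so there is no figure to reproduce. Assumptions: two-sided alpha 0.05, 1:1 allocation, *n* = 20 to 50 analysed per arm, normal change scores.

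**Step 3: PST adds nothing and both arms change by the same amount.** Let *d* be the shared change in SDs of the change score. The paired t-test has noncentrality d√n on n − 1 degrees of freedom; pooled over both arms it has d√(2n) on 2n − 1. At *d* = 0.3:

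- n = 20: 0.3 × √20 = 1.34, significant with probability 0.247; pooled, 0.3 × √40 = 1.90, probability 0.457.
- n = 50: 0.3 × √50 = 2.12, probability 0.548; pooled, 0.3 × √100 = 3.00, probability 0.844.

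For other values of *d*, at n = 20 and n = 50:

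| Shared change *d* | PST arm alone | Both arms pooled |
|---|---|---|
| 0.1 | 0.07, 0.11 | 0.10, 0.17 |
| 0.2 | 0.14, 0.28 | 0.24, 0.51 |
| 0.3 | 0.25, 0.55 | 0.46, 0.84 |
| 0.5 | 0.56, 0.93 | 0.87, 0.999 |

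A two-sample test on change scores rejects in 5% of trials whatever the shared change. In 20,000 simulated trials at n = 50 and d = 0.5 it rejected in 5.1%.

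**Step 4: comparing the two arms' p-values informally.** The arms are independent, so the chance of a significant result in PST but not in Education is P × (1 − P). At d = 0.3 this is 0.247 × 0.753 = 0.186 for n = 20 and 0.548 × 0.452 = 0.248 for n = 50, with no true difference.

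**Step 5: PST prevents a worsening.** Suppose PST stays flat and Education worsens by 0.5 SD of the score. The PST-arm paired test then rejects in 5% of trials, and in the favourable direction in 2.5%. For ANCOVA with baseline-follow-up correlation *r*, the noncentrality is 0.5 × √(n/2) / √(1 − r²). At r = 0.5:

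- n = 20: 0.5 × 3.162 / 0.866 = 1.83, power 0.43.
- n = 50: 0.5 × 5 / 0.866 = 2.89, power 0.82.

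Over n = 20 to 50, power is 0.37 to 0.74 at r = 0.3 and 0.58 to 0.93 at r = 0.7. At r = 0.5 the SD of change equals the SD of the score, and a two-sample test on change scores has power 0.34 to 0.70. ANCOVA has (1 + r)/2 = 0.75 of its variance.

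**The case against.** The best defence is that the text is loosely worded rather than wrong. Intent-to-treat usually implies analysis by randomised group, the before-after differences might be meant as change scores to be compared between arms, and the effect sizes might be between-arm. The authors may have intended this, but the tests they name cannot do it, and intent-to-treat defines a population, not a contrast. The effect size is, strictly, undefined: only before-after differences precede it, and no arm contrast is given.

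Other points have some force:

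- The phrase about all participants appears only in the 6-month sentence and may describe the analysis set rather than pooling. The pooled figures apply only if the arms are combined.
- Maintenance, in Hypothesis 2b, is partly a within-arm question. What is to be maintained, however, is an effect of PST, and that needs the control arm.
- The probabilities depend on assumed inputs. With a shared change of only 0.1 SD, the PST-arm rate is 7% to 11%, not far above 5%.

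None of these supplies a between-arm test.

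**Conclusion.** The concern holds. The tests written for the trial's efficacy hypotheses, including both primary efficacy outcomes, cannot answer them. If they are followed as written, randomisation contributes nothing to the inference. This rests on the text alone and needs no assumed number.

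The size of the error does depend on assumptions. With 20 to 50 per arm and a shared change of 0.3 SD, an ineffective PST would give a significant PST-arm result in 25% to 55% of trials, against 5% for a proper comparison. If PST works by preventing a 0.5 SD worsening, the PST-arm test detects it no more often than chance, while ANCOVA has 43% to 82% power at r = 0.5. The case is complete for Hypothesis 2a. For 2b it applies to the treatment effect, not to the purely descriptive question of change over time. This must be fixed before outcomes are examined by arm.

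**What to change.** Replace the Aim 2 paired tests in section 14 with a between-arm analysis:

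- For each outcome, fit an ANCOVA of the 1-month score on randomised arm and baseline score. Add site, because randomisation is stratified by it. Report the adjusted PST-minus-Education difference with its 95% confidence interval and p-value.
- Do the same at 6 months for Hypothesis 2b, and show the 1-month and 6-month differences side by side so that maintenance can be judged. A mixed model giving the same contrasts would serve equally well.
- If residuals are clearly non-normal, use a rank-based ANCOVA or a bootstrap interval.
- Define the effect size as the between-arm difference divided by the baseline SD, and apply the existing bands to that.
- Keep within-arm changes as description only.

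The cost is plan wording: no new data, visits or participants. Two consequences should be stated openly. A before-after change that looks significant may cease to be so once the control arm is subtracted. Precision may also be limited: at 80% power and two-sided 5%, a two-sample test for a difference of 0.5 SD of the change score needs about 2 × (1.96 + 0.84)² / 0.5² ≈ 63 analysed per arm, and the plan states no sample size.

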3. Concise Summary of Project: Participants are care partners of adults with TBI who are inpatient patients at Zale Lipshy Hospital or Parkland Memorial Hospital. They will complete baseline testing and follow-up testing at 1-month and 6-months post-intervention. They will participate in up to 6 sessions of the Problem Solving Training intervention, delivered in person or via telephone. These data will be used to assess the feasibility of delivering this intervention. These data will also be used for secondary analysis to determine relationships between baseline measures, demographics, and outcomes among care partners of adults with traumatic brain injuries.

4. Study Procedures: This will be a randomized controlled trial, with blocked randomization stratified by performance site, of PST + Education vs Education alone for care partners of adults with TBI admitted to inpatient rehabilitation. Baseline assessment and all intervention sessions will occur during the time the patient with TBI is in inpatient rehabilitation, with the exception of the last intervention session, which can occur via telephone post-discharge. Follow-up assessments will occur at 1-month and 6-months after the completion of the intervention.

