11. Subject Safety and Data Monitoring: A detailed Data and Safety Monitoring Plan will be submitted to the IRB. The study staff (PI, Co-Investigators, research coordinator, interventionist) will be responsible for collecting and recording all data. As results are collected, all Adverse Events will be identified, graded for severity and assigned causality, reported to the required entities, and compiled for periodic review. After assigning causality, the PI will decide the course of action for the study participant. The PI will evaluate all Adverse Events and determine whether the Adverse Event affects the risk/benefit ratio of the study and whether modifications to the protocol or informed consent form are required. Throughout this process, the PI will inform and collaborate with the research team. The plan to monitor participant data and safety will specifically include the following: (1) [name] will inspect collected data; (2) The IRB offices will be contacted if there is an Adverse Event due to participation; (3) the research protocol will be revised if it is determined that the protocol or intervention presents an unforeseen risk to participants; (4) if an event occurs that requires immediate attention and [name] is unavailable, then members of the research team will follow the emergency procedures put in place by the research team, which may include calling emergency medical services. [name] will develop procedures for all data management functions including data quality checks and verification, in collaboration with the TBI Model Systems National Data and Statistical Center. Internal edit and logic checks (e.g., out of range values, internal inconsistencies) will be developed and run quarterly. Descriptive statistics will be calculated and included into quarterly reports to ensure the quality of data and progress of the study.

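### Aim 2 names only paired before-after tests, which cannot compare the randomised arms; the lack of a missing-score rule is a secondary gap

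*Combined protocol and SAP*

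**What the plan says.** Section 14 of the combined protocol and SAP holds the whole Aim 2 analysis. For the first hypothesis: "we will use intent-to-treat analyses to measure the pre-post-test differences in each outcome between baseline and 1-month follow-up using a paired t-test", or a Wilcoxon signed rank test. For the second: "we will use intent-to-treat analyses to measure the pre-post-test differences in each outcome between baseline and 6-month follow-up (all participants) using paired t-tests", with the same rank alternative. Effect-size bands follow (below 0.2 none or minimal, 0.8 and above large), but the text does not say whether they apply within or between arms.

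The question being asked is comparative. Section 4 (Study Procedures) states: "This will be a randomized controlled trial, with blocked randomization stratified by performance site, of PST + Education vs Education alone". In section 1, Hypothesis 2a predicts lower burden and depressive symptoms and better coping "at one-month post discharge more than TBI-specific education alone".

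On follow-up, section 4 states: "Follow-up assessments will occur at 1-month and 6-months after the completion of the intervention". Assessors may work in person or by telephone, or "will send the assessments electronically to the participant through RedCap at baseline, 1-month, and 6-months post-intervention". The nearest text on data handling is in section 11: "Internal edit and logic checks (e.g., out of range values, internal inconsistencies) will be developed and run quarterly". That concerns data quality and gives no rule for an absent score. The non-compliance text in section 14 concerns intervention sessions under Aim 1.

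**The concern.** Care partners are recruited at a time of acute strain, so scores may move over the following months whatever the intervention. A before-after test attributes all of that movement to whatever the group received. Run in the PST arm alone, it can be significant with no PST effect. Run in both arms pooled, it says nothing about PST. Run separately in each arm, it invites the inference that significance in one arm and not the other shows a difference. Randomisation protects only a direct comparison of the arms, and the plan names none.

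The second gap concerns incomplete follow-up. A paired test needs both scores. With no rule stated, a care partner without the follow-up score would most naturally be dropped. At month 6 the test would also make no use of a 1-month score already in hand. How to handle such cases could then be decided after the results are seen.

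**Working it through.** The documents give no sample size, alpha, power, SD, dropout rate or correlations for Aim 2, so there is no planned figure to reproduce. All numbers below rest on labelled assumptions.

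**1. Question against test.** Hypothesis 2a concerns (mean change in PST + Education) minus (mean change in Education alone). The paired t-test examines whether mean change = 0 in whichever group it is run. No two-sample test, analysis of covariance or mixed model appears anywhere in the document. This step needs no assumption about missing data.

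**2. What the paired test does when PST adds nothing.** Assumptions: both arms change by 0.3 baseline SD; baseline to follow-up correlation r = 0.5; two-sided 5%; 25, 40 or 60 per arm.

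- SD of change = √(2(1 − r)) = √(2 × 0.5) = 1, so the standardised change is 0.3.
- Approximate power = Φ(0.3√n − 1.96). For n = 25: Φ(1.50 − 1.96) = 0.32. For n = 40: Φ(1.90 − 1.96) = 0.48. For n = 60: Φ(2.32 − 1.96) = 0.64.
- Simulation with the t distribution (20,000 trials) gives 30%, 46% and 62%.
- PST significant and Education not is p(1 − p): 0.30 × 0.70 = 0.21; 0.46 × 0.54 = 0.25; 0.62 × 0.38 = 0.24. The simulation gives 21%, 25% and 23%.
- A paired test pooling both arms is significant in about 55%, 75% and 90%.
- A two-sample test of change rejects in about 5% at each n.

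**3. Missing scores.** Assumptions: correlations 0.6 (baseline to month 1), 0.65 (month 1 to month 6) and 0.5 (baseline to month 6); higher score = worse; logistic dropout with base rate 30% and log-odds slopes 0.7 and 1.0 per SD, giving 31-33% missing. Entries are bias in baseline-SD units at the two slopes. The model is the mixed model proposed under the fix. Unequal loss means base rates of 30% and 15% in the two arms.

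| Visit; dropout follows | One arm, no true change: complete pairs | Arm contrast, unequal loss, no effect: complete pairs / model | Arm contrast, same rule, true effect −0.5: complete pairs / model |
|---|---|---|---|
| Month 6; 1-month change | −0.11, −0.16 | −0.05, −0.07 / 0.00, 0.00 | +0.02, +0.04 / 0.00, 0.00 |
| Month 6; unseen 6-month change | −0.20, −0.28 | −0.09, −0.12 / −0.05, −0.07 | +0.04, +0.07 / +0.02, +0.04 |
| Month 1; baseline | +0.08, +0.11 | +0.03, +0.05 / 0.00, 0.00 | 0.00 / 0.00 |
| Month 1; unseen 1-month change | −0.16, −0.23 | −0.07, −0.10 / −0.06, −0.08 | +0.04, +0.06 / +0.03, +0.05 |

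- Equal loss, same mechanism, no true effect: the arm contrast is within 0.003 of zero in all 16 settings, for complete pairs and for the model.
- Outcome-related dropout in the PST arm only: the complete-pair arm bias is about the one-arm figure, so it can pass 0.2.
- At lower total loss, the one-arm month-6 bias is −0.04 to −0.09 with 10% missing and −0.07 to −0.17 with 20%.
- Other correlations change the picture. With all three at 0.6 and month-6 dropout driven by the 1-month score, there is no bias. With 0.3, 0.7 and 0.3 (same order), 40% missing and opposite patterns in the two arms, a true contrast of −0.30 appears as −0.57.

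**4. Size of a delta adjustment.** With 32% of PST scores missing and imputed scores worsened by 0.5 SD, the PST mean moves by 0.32 × 0.5 = 0.16 SD. If the worsened 1-month value feeds the 6-month imputation, its coefficient is (0.65 − 0.6 × 0.5)/(1 − 0.6²) = 0.35/0.64 = 0.55. If everyone missing at month 6 also missed month 1 and delta is applied at both visits, the month-6 shift is 0.32 × (0.5 + 0.55 × 0.5) = 0.25 SD.

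**The case against.** The strongest defence is that section 14 is shorthand: the aim, the hypothesis and the intent-to-treat label all imply that changes will be compared between arms, and the effect sizes may be meant as between-arm. That may well be the intention. But both named tests are within-person procedures, no between-arm test is attached to the effect sizes, and an analyst following the text would not produce the contrast.

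The missing-data part is open to several stronger readings that the documents do not support.

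- A reader might infer that missing scores are why there is no arm contrast. They are not; the paired tests lack one with complete follow-up.
- A reader might infer that the plan ignores 1-month scores. Only the 6-month test does. The 1-month test, at the time point of Hypothesis 2a, uses them.
- A reader might infer that the plan prescribes complete pairs or breaches intent-to-treat. Complete pairs is an inference from silence. Analysing people as assigned is not contradicted, the parenthesis in the 6-month sentence may only mean both arms, and imputed scores could be fed into a paired test.
- A reader might take the electronic questionnaires as evidence of high loss. The same sentence offers in-person and telephone assessment, which may help retention. Some loss over 6 months is foreseeable; its size is unknown.
- A reader might carry the one-arm figure of −0.28 SD over to the treatment comparison. That would need outcome-related dropout in one arm only, and no section suggests it.

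It is also fair to say that a mixed model is no cure for missing data. When month-1 dropout follows unseen worsening, the one-arm likelihood bias is −0.13 and −0.18, against −0.16 and −0.23 for complete pairs, so about 80% remains. The precision gain is small: SE inflation of 1.07 against 1.12 with 20% missing at random and an assumed 60 in an arm. The case for the model rests mainly on its supplying the arm contrast.

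**Conclusion.** The Aim 2 analysis is wrong as written: followed exactly, section 14 cannot test Hypothesis 2a. This conclusion comes from the text alone. The 30-62% and 21-25% figures, against about 5% for a between-arm test, illustrate the consequence and depend on the assumed sample sizes, correlation and common 0.3 SD change.

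The missing-score gap is real but secondary. Under the assumed values, its effect on an arm contrast is nil with equal loss, the same mechanism and no true effect. It is mostly below 0.2 SD otherwise, so it would matter chiefly for results near a cut-off. The change should be made before the outcome data are analysed by arm.

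**What to change.** In section 14:

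- **Primary analysis of each outcome.** Fit a longitudinal mixed model to all randomised participants as assigned, using baseline, 1-month and 6-month scores. Include a common baseline mean (or baseline as a covariate), arm-by-visit terms and the site stratum, since allocation uses "blocked randomization stratified by performance site".
- **Hypotheses.** Test 2a by the 1-month arm contrast. Report the 6-month arm contrast for 2b, and say that this is one reading of maintained.
- **Missing scores.** State the missing-at-random assumption and report missing scores by arm and visit.
- **Supportive analyses.** Keep the within-arm paired tests on complete pairs, labelled as supportive. Add a between-arm test of complete-pair change scores, rank-based if they are clearly non-normal.
- **Sensitivity.** Add a simple delta-adjusted multiple imputation that worsens imputed PST scores in steps (for example 0 to 0.5 baseline SD) and reports the step at which the conclusion changes. State whether delta carries forward from month 1 to month 6, because step 4 of the working shows that this alters its size.
- **Effect sizes.** Say that the bands apply to the arm contrast.

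The cost is SAP wording and modest programming; both follow-up scores are already scheduled. One drawback should be acknowledged. If dropout follows a stable unobserved level, complete-pair change is unbiased, while the likelihood estimate in one arm at month 1 is off by about −0.05, −0.07 and −0.11 SD at slopes 0.7, 1.0 and 1.5. At the same slopes, complete pairs are off by +0.08, +0.11 and +0.15 SD when dropout follows baseline. Neither approach is safe under every mechanism, which is why both the complete-pair comparison and the delta analysis are kept.
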